Study protocol

NCT03232801

Title: A Mindfulness-Based Intervention for Older Women with Low Sexual Desire

Version date: August 1, 2022

Study Rationale

Sex is a fundamental component of overall well-being for many adults. Individuals who maintain a healthy sex life with aging live longer and have high quality of life. However, sexual function problems are common, particularly among midlife women; 39% of this population struggles with low sexual desire. This can affect not only a woman's sex life, but also negatively impact on psychosocial functioning and relationships.

Despite success in developing treatment for men, there has been a lack of treatment options for women. An increasingly accepted model of female sexual response emphasizes both physiologic and psychologic aspects of female sexual function. Pharmacologic treatments that only target physiologic response will only help a subset of women. In contrast, behavioral interventions have the potential to target both physiologic and psychological aspects of female sexual function. Using this rationale, this study will look at the use of a mindfulness study to improve sexual function in midlife women. Female sexual dysfunction is associated with sexually-related anxiety, autonomic nervous system imbalance, negative body image, discursive negative thoughts that distract during sex, and poor sleep.

Using this rationale, this study will look at the use of a mindfulness study to improve sexual function in midlife women. Mindfulness, a concept that emphasizes in-the-moment focus and non-judgmental bodily awareness, can target all these aspects of sexual dysfunction simultaneously by decreasing anxiety, improving autonomic imbalance, enhancing body image, reducing distracting thoughts, and improving sleep.

Treating sexual dysfunction will result in improvements in women's sexuality and can have the opportunity to go beyond sex to improve relationships and overall quality of life in aging adults. At least 85% of women in the intervention group will indicate somewhat or very satisfied on a measure of the intervention satisfaction.

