Following the screening, participants will be sent a survey link to complete all the baseline activities. Once the intervention starts, participants will attend a weekly virtual session with other members of their group (control vs variable). These sessions will last for six weeks at approximately two hours each. In these sessions, they have the possibility of interacting with members of their group and with the leaders of each group. However, group participation is up to the participant; they are able to share as little or as much as they feel comfortable. Following the completion of the sessions, a survey will be sent to participant. These surveys will be identical to the baseline surveys, excluding the surveys on Demographics, Relationship Variables, Frequency of Sexual Activities, and Medical Variables. There will also be an Acceptability of Intervention survey sent out at the finish of the sessions. Participants will have one week to fill out and return the surveys, which will be tracked through RedCap.

At the 12 week mark, a final set of surveys will be sent out, identical to the baseline surveys, excluding the surveys on Demographics, Relationship Variables, Frequency of Sexual Activities, and Medical Variables. Participants will have one week to fill out and return the surveys, which will be tracked through RedCap.

Interventionist Training and Tracking

To ensure the completion of all surveys, in the week the survey is disseminated, progress will be monitored using RedCap. All surveys need to be returned within the week they are sent out so if progress is not being made by a participant, the RA will reach out up to three different times to send reminders and check in. The three contact points can be made via different methods, including through email and phone call.

Discontinuation/Withdrawal

An investigator may discontinue a participant from the study for the following reasons:

- Significant study intervention non-compliance, unless varying compliance is an aspect of the study objectives
- Lost-to-follow up
- Any event or medical condition or situation occurs such that continued collection of follow-up study data would not be in the best interest of the participant or might require an additional treatment that would confound the interpretation of the study
- The participant meets an exclusion criterion (either newly developed or not previously recognized) that precludes further study participation

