Participants are allowed to withdraw at any time for any reason. Data up until the point a participant discontinued the study will be included in the study. Participants will not continue with surveys when participation is discontinued.

If a participant misses more than 2 meetings, they are withdrawn from the study. They are still eligible for payment if they completed the first survey. If there are further six-week sessions, a participant can move to a later session that may fit their schedule.

Loss to Follow-Up

The following actions must be taken if a participant fails to return their surveys in the correct amount of time:

- The site will attempt to contact the participant, remind them of the studies they have left to complete, counsel the participant on the importance of maintaining the assigned visit schedule, and ascertain if the participant wishes to and/or should continue in the study
- Before a participant is deemed lost to follow-up, the investigator or designee will make every effort to regain contact with the participant. The investigator or designee will make up to 3 different attempts at contact with the participant. These attempts will include reaching out via phone or email.
- Should the participant continue to be unreachable, they will be considered to have withdrawn from the study with a primary reason of lost to follow-up.

Weekly Meetings

Meetings for each group will be held on separate days. Following recruitment, a survey will be sent out to the participants to each group. Any survey system can be used to generate the surveys to gauge interest in the best day and time for the group (Qualtrics was used). Make sure that each group has a separate survey (i.e. an availability survey for both the mindfulness (experimental) and educational (control) group).

Give the groups around one week to answer, sending out 1-2 reminders. Once a day and time is decided on, meetings can begin. An email can be sent to participants with the upcoming dates and the Zoom link. To ensure participants remember the meeting, an email should be sent every week, 12-24 hours before the meeting with the zoom link.

Meetings are held every week for six weeks total. Meeting length is variable, but participants should prepare for a two-hour meeting.

At each meeting, a research assistant should take attendance and keep track of who is coming to the meetings. This is important to record to ensure participants are making it to at least 4 meetings.

Payment

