NCT03232801

Title: A Mindfulness-based Intervention for Older Women with Low Sexual Desire

Date: August 1, 2022

Statistical analysis:

We assessed satisfaction and likelihood of recommending the group to another woman with low libido at 7 weeks (primary outcome). We assessed sexual function [Female Sexual Function Index (FSFI)] and sexual distress [Female Sexual Distress Scale-Revised (FSDS-R)] at 12 weeks (exploratory outcomes). We used chi squared statistics to examine differences in primary outcomes between groups. We constructed linear regression models to compare changes in FSFI and FSDS-R from baseline to 12 weeks for each group.

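### The primary 7-week satisfaction outcome is not collected, in their allocated series, from women withdrawn for missing more than 2 of the 6 meetings, so the reported proportion describes a population of attenders that the documents do not declare

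*Protocol*

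**What the plan says.** **Attendance rule.** Under Discontinuation/Withdrawal the protocol says "If a participant misses more than 2 meetings, they are withdrawn from the study". Weekly Meetings fixes six meetings and has attendance recorded against a minimum of four, which agrees with that threshold.

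**Surveys after discontinuation.** The same section says "Participants will not continue with surveys when participation is discontinued" and also "Data up until the point a participant discontinued the study will be included in the study". It then allows a move to a later series, if one is held.

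**When the outcome is measured.** Under Administration: "There will also be an Acceptability of Intervention survey sent out at the finish of the sessions". The 12-week set is described as the baseline set with some forms removed; acceptability is not listed in it.

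**Analysis.** The SAP's primary outcome is satisfaction and likelihood of recommending the group at 7 weeks. On the analysis it says "We used chi squared statistics to examine differences in primary outcomes between groups". For the exploratory outcomes it says "We constructed linear regression models to compare changes in FSFI and FSDS-R from baseline to 12 weeks for each group". It states no analysis population, denominator or missing-data rule.

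**The only satisfaction benchmark.** The protocol's Study Rationale says "At least 85% of women in the intervention group will indicate somewhat or very satisfied on a measure of the intervention satisfaction".

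**The concern.** The trial's primary question is whether women find the group acceptable. Attendance plausibly reflects acceptability, yet the written rules let attendance decide who is asked. A woman who stops coming leaves follow-up as well as the sessions, and she leaves before the single measurement of the primary outcome.

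What is at stake is the meaning of the reported proportion. The 85% statement refers to women in the intervention group, whereas the figure the rules can produce refers to responders who attended at least 4 of 6 meetings. Satisfaction among attenders is a legitimate thing to report, but a reader needs to be told that this is what it is, and how many women in each arm lie outside it. The 12-week FSFI and FSDS-R change scores are restricted in the same way: a withdrawn woman keeps her baseline value and has no 12-week value.

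**Working it through.** The documents give no sample size, withdrawal rate or non-response rate, so there is no planned figure to reproduce. The first two steps are a reading of the text; the others are illustrations on assumed inputs.

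**1. Timing.** Withdrawal needs a third absence among six meetings, so it can occur at meeting 3, 4, 5 or 6. At meetings 3 to 5 it clearly precedes the acceptability survey. At meeting 6 it coincides with the end of the sessions; the documents do not say which comes first, but surveys stop once a woman is discontinued.

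**2. Does anything else supply the rating?**
- Keeping data up to discontinuation preserves baseline, but no satisfaction rating exists by then.
- The three contact attempts (Interventionist Training and Tracking; Loss to Follow-Up) concern women who were sent surveys and did not return them.
- The optional interview is not the survey.
- A move to a later series could supply a rating, but the protocol does not say that movers are surveyed afterwards, nor which series would count.

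**3. Bounds for one arm.** Let p be the proportion satisfied among responders and u the fraction of randomised women who never respond. The all-randomised rate lies between p(1 − u), if no non-responder is satisfied, and p(1 − u) + u, if all are. Take p = 85% from the Study Rationale and assume u:

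| u (assumed) | Lower bound | Upper bound |
|---|---|---|
| 10% | 0.85 × 0.90 = 76.5% | 76.5% + 10% = 86.5% |
| 20% | 0.85 × 0.80 = 68.0% | 68.0% + 20% = 88.0% |

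**4. Bias for one arm.** Reported rate minus all-randomised rate = u × g, where g is satisfaction among responders minus satisfaction among non-responders.
- g = 0: no bias, whatever u is.
- g = 40 points: 0.10 × 40 = 4 points too high, or 0.20 × 40 = 8 points too high.
- g = −15 points (all non-responders satisfied, 100% against 85%): 0.10 × 15 = 1.5 points too low, or 0.20 × 15 = 3 points too low. These match the upper bounds above.

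**5. One session group of 15** (the top of the stated 12 to 15 range, not an arm total). Suppose 3 are withdrawn and give no rating, and 11 of the other 12 are satisfied. The reported figure is 11/12 = 91.7%. Over all 15 it lies between 11/15 = 73.3% and 14/15 = 93.3%.

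**6. Between arms.** Bias in the difference = uA × gA − uB × gB. With a 40-point gap in both arms:
- 20% lost in each: 8 − 8 = 0 points.
- 30% against 10%: 12 − 4 = +8 points; reversed, −8 points.

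Scoring every non-responder as not satisfied in both arms does not bound the difference. With p = 85% and u = 10% in each arm, that scoring gives 76.5% − 76.5% = 0. Opposite extremes in the two arms give 76.5% − 86.5% = −10 points, or +10 points the other way. With u = 20% in each arm the range is 68.0% − 88.0% = −20 points to +20 points.

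**The case against.** **The specified test may be unaffected.** The SAP's primary analysis compares arms, the attendance rule and number of meetings are the same in both, and the control is an active one. Nothing in the documents shows differential withdrawal. This stands. A reader might infer that the chi-squared comparison is biased towards the intervention; the documents do not support that, and the 8-point figures need an invented imbalance and an invented gap.

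**Absence need not mean dissatisfaction.** The protocol itself links moving to a later series with fitting a woman's schedule. This also stands. A reader might infer that satisfaction is necessarily overstated; no bias and understatement are equally compatible with the text.

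**The 85% figure is not an SAP criterion.** Correct: it is one sentence in the rationale, with no time point or denominator. It is used here only as a benchmark that a reader is likely to apply.

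**A woman who attended little has little to rate.** This is a fair argument for reporting satisfaction among attenders. It supports declaring that population; it does not support leaving it unstated.

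**The discontinuation rules.** A reader might infer a contradiction between the general list, under which an investigator may discontinue a woman for non-compliance, and the attendance rule, which is automatic. The documents do not support that reading: a specific threshold under a general power is ordinary drafting.

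**The trial may be over.** The SAP is written in the past tense. If data collection has closed, only reporting can change. That limits the remedy but leaves the undeclared population as it is.

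**Conclusion.** The point holds as a gap in outcome collection created by the written rules, together with an analysis population that is not stated. It should be fixed. That poor attenders give no 7-week rating in their allocated series follows from the text, apart from the unclear ordering when the third absence is the last meeting. The size and direction of any resulting bias do not follow from the text.

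The numerical ranges assume 10% or 20% of women never responding and 85% satisfaction among responders. They extend much further below 85% than above it because responders are already near the ceiling; that asymmetry is not evidence that withdrawn women were dissatisfied. Confidence is medium, because without counts by arm nobody can tell whether the gap is trivial or large.

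**What to change.** **If surveys are still open.** Leave the session attendance rule unchanged, but separate leaving the sessions from leaving follow-up:
- Send the 7-week and 12-week surveys to every randomised woman whatever her attendance, unless she withdraws consent to contact or further data collection is judged not in her best interest, a ground the protocol already recognises.
- Analyse each woman once, in her randomised arm.
- State in advance which series' rating counts for a woman who moves, since she could then have two.

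**If surveys have closed:**
- Report by arm the numbers randomised, withdrawn (with reason), moved to a later series and responding, from the attendance and REDCap records.
- Describe the main proportion as applying to responders who attended at least 4 meetings.
- For each arm give both bounds over all randomised women: non-responders all not satisfied, and all satisfied.
- Give the resulting range for the between-arm difference, including opposite extremes in the two arms.

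**Cost.** With open surveys: a short amendment, a few SAP lines, and up to 2 × $25 + $25 = $75 per additional woman followed (two further assessments plus the completion bonus), for example 3 × $75 = $225 for three women. It would be more if a mover is paid for a second set of surveys. The survey and reminder process already exists. With closed surveys there is only analysis and reporting effort. Either way, the satisfaction figure may look less favourable.

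### Read as written, a woman who cannot be reached about her overdue post-session survey is withdrawn and so also loses her 12-week FSFI and FSDS-R, which could still be collected.

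*Protocol*

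**What the plan says.** **Survey window (protocol, Administration).** The post-session survey and the 12-week survey have the same window: "Participants will have one week to fill out and return the surveys, which will be tracked through RedCap". Interventionist Training and Tracking adds "All surveys need to be returned within the week they are sent out" and, for a woman who is not progressing, "the RA will reach out up to three different times to send reminders and check in".

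**Trigger (protocol, Loss to Follow-Up).** The procedure opens with "The following actions must be taken if a participant fails to return their surveys in the correct amount of time". It is not limited to the last survey, and no minimum number of missed surveys is required. Staff remind and counsel the woman and find out whether she wishes to, or should, stay in. Then: "The investigator or designee will make up to 3 different attempts at contact with the participant".

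**Consequence (same section).** For women who still cannot be reached: "they will be considered to have withdrawn from the study with a primary reason of lost to follow-up".

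**After discontinuation (protocol, Discontinuation/Withdrawal).** "Participants will not continue with surveys when participation is discontinued". Data collected up to that point are kept. The same section lists loss to follow-up among the reasons for which the investigator *may* discontinue a participant.

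**Analysis (SAP, Statistical analysis).** Satisfaction and likelihood of recommending the group, at 7 weeks, are primary. FSFI and FSDS-R at 12 weeks are exploratory and are analysed by linear regression on change from baseline. No method for missing scores is given.

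**The concern.** Being unreachable is often temporary. The protocol turns it into a permanent status at the first survey after the sessions, with one assessment still to come. A woman may have attended every session, gone out of contact for a while, and be quite willing to answer at week 12. Under the rule she is not asked.

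The loss is avoidable. The 12-week comparison uses two scores per woman, at baseline and at 12 weeks. The baseline is already held, and the 12-week survey would go out through a system already in use. Groups are small, roughly 12 to 15 women, so each record counts.

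The post-session package also contains the acceptability survey, so non-response at that point could be related to how a woman felt about her group and could differ between arms. The documents neither show nor exclude this. If it happens, the rule carries the selection forward into the 12-week comparison.

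**Working it through.** The plan has no sample size, power or dropout figure on this point, so there is nothing of its own to reproduce. The check is a reading of the rule followed by an illustration.

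**1. The chain**

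- Post-session survey not returned within one week: the loss-to-follow-up procedure starts.
- Up to three attempts, woman still unreachable: she is considered withdrawn.
- Withdrawn for loss to follow-up, which is a listed reason for discontinuation: no further surveys.
- No 12-week survey: no 12-week score, so no change from baseline for FSFI or FSDS-R.

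Nothing in either document exempts the post-session survey or provides for sending the 12-week survey to such a woman. The one loose link is the investigator's option under Discontinuation/Withdrawal (*may*), set against the automatic status under Loss to Follow-Up.

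**2. Precision**

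Assumed inputs: 13 women per arm (within the protocol's 12 to 15), 2 per arm unreachable at week 7, equal variances, everyone else responding. The standard error of the difference is proportional to sqrt(2/n), with n the number per arm analysed.

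- Under the rule, n = 11.
- If both women would have answered at week 12, n = 13 without the rule. Ratio sqrt(13/11) = 1.087, an increase of 8.7%.
- If one of the two would have answered, n = 12 without the rule. Ratio sqrt(12/11) = 1.044, an increase of 4.4%.
- If neither would have answered, the rule costs nothing.

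Across the protocol's group sizes, with 2 per arm unreachable:

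| Per arm | One would answer | Both would answer |
|---|---|---|
| 12 | sqrt(11/10): 4.9% | sqrt(12/10): 9.5% |
| 13 | sqrt(12/11): 4.4% | sqrt(13/11): 8.7% |
| 15 | sqrt(14/13): 3.8% | sqrt(15/13): 7.4% |

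**3. Number of records**

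For one pair of groups (24 to 30 women), let m be the share unreachable at week 7 and r the share of those who would answer at week 12. Both are assumed: m from 5% to 20%, r from 25% to 75%.

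- 12-week surveys not sent: N × m, from 24 × 0.05 = 1.2 to 30 × 0.20 = 6.0.
- Of these, recoverable: N × m × r, from 1.2 × 0.25 = 0.3 to 6.0 × 0.75 = 4.5.

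At m = 20% and r = 50%, n per arm is 9.6 under the rule and 10.8 without it (12 per group), or 12.0 and 13.5 (15 per group). Assume a two-sided 5% level and 80% power. The detectable difference, (1.960 + 0.842) × sqrt(2/n), then moves from 1.28 to 1.21 SD, or from 1.14 to 1.08 SD.

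**4. Bias**

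Suppose that, in one arm only, the two women lost are exactly the two lowest of 13 on a trait correlated 0.5 with the outcome, and both were recoverable. The expected lowest two of 13 standard normal values are about -1.67 and -1.16.

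- The mean of the other 11 is raised by (1.67 + 1.16)/11 = 0.257.
- On the outcome scale this is 0.5 × 0.257 = 0.129, about 0.13 SD.
- If selection is itself only correlated 0.5 with that trait, the shift roughly halves: 0.5 × 0.129 = 0.064 SD.
- For comparison, the standard error with 13 and 11 women is sqrt(1/13 + 1/11) = 0.41 SD. A shift of 0.13 SD is about a third of it.

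**The case against.** The strongest case on the other side is that the rule is narrower and softer than it looks, and that little depends on it.

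- *A reader might infer that missing one window and three reminders is enough for withdrawal.* It is not. The woman must stay unreachable. One who is reached but late is reminded, counselled and asked about continuing, and is not withdrawn automatically. No deadline is set for the attempts, so a short absence need not end in withdrawal. This objection stands and limits the point. On the other side, the text says up to three attempts, so fewer could suffice. It is also unclear whether the in-window reminders and the later attempts are the same three.
- *A reader might infer that a survey returned on day 8 is discarded.* Neither document says so. The one-week requirement sits with the instruction to send reminders, and overdue women are reminded of what remains to be completed, which suggests that late returns are wanted.
- *The investigator has discretion.* True of Discontinuation/Withdrawal, but Loss to Follow-Up states the withdrawn status without discretion. A permanent bar is the plainest reading, though not the only one. The conflict is a reason to clarify and does not ensure that she is asked at week 12.
- *The stakes are modest.* FSFI and FSDS-R are exploratory, and the 7-week primary outcome is already missing for this woman, so the rule does no further harm there. Payment for each assessment, with an extra payment for completing all three, and active tracking should keep numbers low. All of this stands. It bears on how often the rule takes effect and does not alter what the rule does.
- *It is tempting to say that dissatisfied women are the ones who fail to respond.* The documents offer no evidence for it. It is a possibility and nothing more.

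**Conclusion.** The point holds in this form: as written, a woman who remains unreachable about her post-session survey is withdrawn and receives no 12-week survey, although the SAP's 12-week analysis could have used her. The two sections also disagree on whether withdrawal for loss to follow-up is optional or automatic.

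The effect on precision is small to moderate: about 4.4% on the standard error if half of the unreachable women would have answered, and 8.7% at most, for 13 per arm with 2 per arm unreachable. Any bias is unknown in size and direction. The 0.13 SD figure requires fully deterministic selection, loss in one arm only and complete recoverability, so it is an upper illustration and not an estimate. All non-response, recovery and correlation values are assumptions. The number of cohorts and the total sample size are not stated either. Because the outcomes are exploratory, this is a change that should be made, and it does not threaten the primary analysis.

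**What to change.** Change the protocol as follows.

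1. Send the 12-week survey to every randomised woman who has not withdrawn consent, whether or not the 7-week survey came back.
2. Classify a woman as lost to follow-up only after the 12-week survey has also been missed.
3. Make Discontinuation/Withdrawal and Loss to Follow-Up agree on whether loss to follow-up leads to discontinuation by choice or automatically, and say whether the in-window reminders count among the three attempts.
4. If late surveys arrive, record the return date, include them in the main analysis, and repeat the analysis with in-window surveys only as a sensitivity check.

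The cost is a sentence or two of protocol text and invitations through the existing REDCap set-up. The downside is slightly more spread in assessment dates, which the sensitivity analysis addresses. Voluntary withdrawal is untouched. If follow-up is already complete, the sponsor can still report, by arm, how many women were never sent the 12-week survey for this reason.

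### Attendance, withdrawal and survey return are recorded in both arms, but the SAP plans no by-arm analysis of them, while the 7-week primary outcome comes only from women who were not withdrawn for missed meetings

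*Protocol*

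**What the plan says.** **Attendance.** The programme has six sessions (Protocol, Weekly Meetings): "Meetings are held every week for six weeks total". Both arms hold meetings, and the record covers each one: "At each meeting, a research assistant should take attendance and keep track of who is coming to the meetings". The only purpose given is this: "This is important to record to ensure participants are making it to at least 4 meetings".

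**Withdrawal.** Under Discontinuation/Withdrawal: "If a participant misses more than 2 meetings, they are withdrawn from the study". The same section says: "Participants will not continue with surveys when participation is discontinued". It also keeps earlier data: "Data up until the point a participant discontinued the study will be included in the study". A woman may instead move to a later six-week session; how her attendance is then counted is not stated.

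**Other process records.** Survey return is tracked in RedCap (Protocol, Administration). Unreachable women are recorded as withdrawn, with loss to follow-up as the reason (Protocol, Loss to Follow-Up).

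**Outcome and analysis.** The acceptability survey goes out after the sessions finish (Protocol, Administration). The SAP names satisfaction and likelihood of recommending at 7 weeks as primary, and says: "We used chi squared statistics to examine differences in primary outcomes between groups". The Protocol (Study Rationale) sets a target of at least 85% of the intervention group somewhat or very satisfied. Neither document says whether that percentage, or the chi-squared comparison, is taken over randomised women or over respondents. The SAP mentions attendance, withdrawal and survey return nowhere.

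**The concern.** Attendance decides who supplies the primary outcome. A woman who stops coming is withdrawn before the acceptability survey is sent and is not surveyed afterwards. Keeping her earlier data does not help, because the outcome is measured later. Women who leave are plausibly less satisfied than those who stay, although the documents give no figure on this.

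If one arm loses more women than the other, the planned comparison sets those who stayed in one arm against those who stayed in the other. A programme that many women leave could then be reported as equally acceptable, and could meet the 85% target, without the plan requiring the loss to be shown. The records needed to show it are already being made.

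**Working it through.** The documents give no sample size, expected attendance or dropout rate, so there is no design figure to reproduce. All counts in steps 2 to 5 are assumptions. They use the stated group size of roughly 12-15 (Protocol, Strategies for Recruitment and Retention) as the number per arm, which is not a stated total sample size.

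**1. Consistency of the attendance rule.** 6 meetings − 2 permitted misses = 4, which agrees with the 4-meeting check. Attending at least 4 of 6 therefore separates women kept from women withdrawn under this rule, within the assigned session.

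**2. Main illustration, 15 randomised per arm.** Assume 4 mindfulness women and 1 control woman are withdrawn for missed meetings, everyone else responds, and one respondent per arm is not satisfied.

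| Quantity | Mindfulness | Control | Difference | Test |
|---|---|---|---|---|
| Satisfied, among respondents | 10/11 = 90.9% | 13/14 = 92.9% | −1.9 points | chi-squared (uncorrected) p = 0.86 |
| Attended at least 4 of 6, all randomised | 11/15 = 73.3% | 14/15 = 93.3% | −20 points | Fisher p = 0.33; Newcombe 95% CI about −46 to +8 |
| Satisfied, all randomised, withdrawn counted as not satisfied | 10/15 = 66.7% | 13/15 = 86.7% | −20 points | Fisher p = 0.39 |

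The first row is the planned comparison if respondents are the denominator. In the mindfulness arm the 85% target is met among respondents (91%) and missed among all randomised women (67%).

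**3. A more extreme illustration.** Let 10/15 versus 15/15 attend at least 4 meetings, with 9/10 versus 13/15 of respondents satisfied. The respondent comparison is 90% versus 87%, p = 0.80. The attendance comparison is 67% versus 100%, Fisher p = 0.042.

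**4. How much loss the 85% target tolerates.** Over all randomised women, 0.85 × 15 = 12.75, so 13 must be satisfied and at most 15 − 13 = 2 can be lost. For 12 women, 0.85 × 12 = 10.2, so 11 must be satisfied and at most 1 can be lost. Over respondents the target survives heavy loss:

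| Assumed loss | n = 15: respondents → randomised | n = 12: respondents → randomised |
|---|---|---|
| about 30% | 10/11 = 91% → 10/15 = 67% | 7/8 = 88% → 7/12 = 58% |
| about 40% | 8/9 = 89% → 8/15 = 53% | 6/7 = 86% → 6/12 = 50% |

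**5. What an attendance test could detect.** For true proportions of 90% versus 60% at an assumed two-sided 0.05, exact Fisher power is 0.33 with 15 per arm and 0.23 with 12 per arm (normal approximation 0.47 and 0.39). At this size the comparison can be an estimate with an interval, not a powered test.

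**The case against.** The strongest reply is that satisfaction is the chosen measure of acceptability, with its own survey and target, and that attendance is only a proxy. Each arm meets on a separate day fixed by its own availability poll (Protocol, Weekly Meetings), so an attendance gap may reflect scheduling. The loss figures are assumed, and the main illustration is inconclusive on its own numbers. All of this stands. It argues for reporting attendance beside satisfaction, with reasons for withdrawal and an interval; it does not argue for leaving it out.

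A reader might also infer stronger points that the documents do not support:

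- **That the trial cannot see an arm losing its women.** Withdrawal status, loss to follow-up and survey return are recorded, and the planned table of respondents would itself show 11 versus 14. What is missing is a planned by-arm report.
- **That attendance is the only objective measure, or is fully observed.** Withdrawal and survey return are objective too. The 0-6 count is cut short by the withdrawal rule, so later zeros may be imposed rather than chosen, and it is undefined for women who move to a later session.
- **That the Protocol makes compliance a study objective.** The relevant item in Discontinuation/Withdrawal reads: "Significant study intervention non-compliance, unless varying compliance is an aspect of the study objectives". This is a conditional exception in a list of reasons for discontinuation, and neither document names compliance as an objective.

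**Conclusion.** The concern holds as a gap in the analysis plan. The 7-week acceptability result is conditional on not having been withdrawn for missed meetings, and the SAP neither sets a denominator nor plans a by-arm account of who was lost. The plan as written therefore allows an acceptability claim in the presence of unreported unequal loss.

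The size cannot be fixed from the documents. With 15 per arm and the assumed counts, a 2-point difference among respondents sits beside a 20-point difference in attendance, and satisfaction in the mindfulness arm falls from 91% to 67% when all randomised women are the base. The 67% depends on counting every withdrawn woman as not satisfied, which is a worst case for those women. If loss is small and equal between arms, the respondent result would change little. Whether the withdrawal rule is appropriate is not judged here.

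**What to change.** Add the following to the SAP, for all randomised women by assigned arm:

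1. The proportion attending at least 4 of 6 meetings of the originally assigned session, with the between-arm difference and 95% CI.
2. Withdrawals with reasons, and the proportions returning the 7-week and 12-week surveys.
3. Meetings attended (0-6) as a descriptive summary, stating that the count is truncated at withdrawal and giving a counting rule for women who move to a later session.
4. Beside the respondent result, a sensitivity analysis of satisfaction, including the 85% target, over all randomised women, with withdrawn or non-responding women counted as not satisfied.

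State that any acceptability conclusion will be reported together with these items, as estimates rather than powered tests, and that attendance may also reflect each arm's meeting schedule.

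The cost is a few lines of SAP text and code on data already recorded. No change to trial conduct is needed. The downside is that the acceptability result may look less favourable.
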